10.2.5. Reporting of SAEs to GSK

SAE Reporting to GSK via Electronic Data Collection Tool

• The primary mechanism for reporting SAEs to GSK will be the electronic data collection tool.• If the electronic system is unavailable, then the site will use the paper SAE data collection tool (see next section) to report the event within 24 hours.• The site will enter the SAE data into the electronic system as soon as they become available.• The investigator or medically qualified subinvestigator must show evidence within the eCRF (e.g., check review box, signature, etc.) of review and verification of the relationship of each SAE to study intervention/study participation (causality) within 72 hours of SAE entry into the eCRF.• After the study is completed at a given site, the electronic data collection tool will be taken offline to prevent the entry of new data or changes to existing data.• If a site receives a report of a new SAE from a study participant or receives updated data on a previously reported SAE after the electronic data collection tool has been taken offline, then the site can report this information on a paper SAE form (see next section) or to the medical monitor by telephone.• Contacts for SAE reporting can be found in the Study Reference Manual. Complete the SAE form and email it to the GSK Case Management Group (CMG) group mailbox: [contact].

SAE Reporting to GSK via Paper Data Collection Tool

• Email transmission of the SAE paper data collection tool is the preferred method to transmit this information to the medical monitor or the SAE coordinator.• In rare circumstances and in the absence of facsimile equipment, notification by telephone is acceptable with a copy of the SAE data collection tool sent by overnight mail or courier service.• Initial notification via telephone does not replace the need for the investigator to complete and sign the SAE data collection tool within the designated reporting time frames.• Contacts for SAE reporting can be found in the Study Reference Manual. Complete the SAE form and email it to the GSK CMG group mailbox: [contact].

Assessment of Intensity

- The investigator will make an assessment of intensity for each AE/SAE/device deficiency reported during the study and assign it to one of the following categories:
- Mild: An event that is easily tolerated by the participant, causing minimal discomfort and not interfering with everyday activities.
- Moderate: An event that causes sufficient discomfort and interferes with normal everyday activities.
- Severe: An event that prevents normal everyday activities. An AE that is assessed as severe should not be confused with an SAE. Severe is a category used for rating the intensity of an event; both AEs and SAEs can be assessed as severe.
- An event is defined as “serious” when it meets at least one of the predefined outcomes as described in the definition of an SAE, not when it is rated as severe.
- Other measures to evaluate AEs and SAEs may be utilized (e.g., National Cancer Institute Common Terminology Criteria for Adverse Events [NCI-CTCAE]).

Assessment of Causality

- The investigator is obligated to assess the relationship between study intervention and each occurrence of each AE/SAE/device deficiency.
- A “reasonable possibility” of a relationship conveys that there are facts, evidence, and/or arguments to suggest a causal relationship, rather than a relationship, cannot be ruled out.
- The investigator will use clinical judgment to determine the relationship.
- Alternative causes, such as underlying disease(s), concomitant therapy, and other risk factors, as well as the temporal relationship of the event to study intervention administration will be considered and investigated.
- The investigator will also consult the IB or Product Information, for marketed products in his/her assessment.
- For each AE/SAE/device deficiency, the investigator **must** document in the medical notes that he/she has reviewed the AE/SAE/device deficiency and has provided an assessment of causality.
- There may be situations in which an SAE has occurred and the investigator has minimal information to include in the initial report to GSK. However, it is very important that the investigator always makes an assessment of causality for every event before the initial transmission of the SAE data to GSK.
- The investigator may change his/her opinion of causality in light of follow-up information and send an SAE follow-up report with the updated causality assessment.
- The causality assessment is one of the criteria used when determining regulatory reporting requirements.

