3. OBJECTIVES AND ENDPOINTS

Objectives	Endpoints
Primary: To characterize corneal epitheliopathy in participants treated with belantamab mafodotin	Primary: Pathologic characteristics and composition of corneal epithelial changes obtained by impression cytology (IC) or SK in participants treated with belantamab mafodotin
Secondary: 
• To correlate clinical data, including visual acuity and symptoms, as well as grade and appearance of corneal changes on imaging, with histopathologic findings• Safety profile of the impression cytology or SK procedure	Secondary: 
• Results of analysis of clinical/imaging data with histopathologic findings• AEs associated with the impression cytology or SK procedure

CCI

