8.1.3. Time Period and Frequency for Collecting AE and SAE Information

- All SAEs related to the IC or SK procedure only will be collected from the start of intervention until the last follow-up visit at the time points specified in the SoA. However, any SAEs assessed as related to study participation (e.g., study intervention, protocol-mandated procedures, invasive tests) will be recorded from the time a participant consents to participate in the study.
- AEs related to the IC or SK procedure only will be collected from the start of intervention until the last follow-up visit at the time points specified in the SoA (Section [1.3](#)).
- Medical occurrences that begin before the start of study intervention but after obtaining informed consent will not be collected.
- SAEs related to the IC and SK procedure will be recorded and reported to the sponsor or designee immediately, and under no circumstance should this exceed 24 hours, as indicated in [Appendix 2](#) . The investigator will submit any updated SAE data to the sponsor within 24 hours of it being available.
- Investigators are not obligated to actively seek information on AEs or SAEs after the conclusion of study participation. However, if the investigator learns of any SAE, including a death, at any time after a participant has been discharged from the study, and he/she considers the event to be reasonably related to the study intervention or study participation, the investigator must promptly notify the sponsor.

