
The investigator is obligated to assess the relationship between study intervention and each occurrence of each AE/SAE.
 
 A "reasonable possibility" of a relationship conveys that there are facts, evidence, and/or arguments to suggest a causal relationship, rather than a relationship, cannot be ruled out. The investigator will use clinical judgment to determine the relationship. Alternative causes, such as underlying disease(s), concomitant therapy, and other risk factors, as well as the temporal relationship of the event to study intervention administration will be considered and investigated.

- The investigator will also consult the IB and/or Product Information, for marketed products, in his/her assessment.
- For each AE/SAE, the investigator **must** document in the medical notes that he/she has reviewed the AE/SAE and has provided an assessment of causality.
- There may be situations in which an SAE has occurred and the investigator has minimal information to include in the initial report to GSK. However, **it is very important that the investigator always makes an assessment of causality for every event before the initial transmission of the SAE data to GSK.**
- The investigator may change his/her opinion of causality in light of follow-up information and send an SAE follow-up report with the updated causality assessment.
- The causality assessment is one of the criteria used when determining regulatory reporting requirements.

Follow-up of AEs and SAEs

- The investigator is obligated to perform or arrange for the conduct of supplemental measurements and/or evaluations as medically indicated or as requested by GSK to elucidate the nature and/or causality of the AE or SAE as fully as possible. This may include additional laboratory tests or investigations, histopathologic examinations, or consultation with other health care professionals.
- New or updated information will be recorded in the originally submitted documents.
- The investigator will submit any updated SAE data to GSK within 24 hours of receipt of the information.

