17.2. SECONDARY SAFETY ENDPOINTS

17.2.1. ADVERSE EVENTS

Adverse Events (AEs) related to the IC or SK procedure only will be collected from the start of intervention until the last follow-up visit at the time points specified in the schedule of activities (Section 3.2).

All Serious Adverse Events (SAEs) related to the IC or SK procedure only will be collected from the start of intervention until the last follow-up visit at the time points specified in the schedule of activities (Section 3.2). However, any SAEs assessed as related to study participation (e.g., study intervention, protocol-mandated procedures, invasive tests) will be recorded from the time a participant consents to participate in the study.

AEs and SAEs will be presented on the ICSK population and coded using MedDRA version 23.0 or above.

An overall summary table of number of participants within each of the categories described below, will be provided by method of tissue collection (impression cytology/superficial keratectomy) summarizing:

- Participants with at least one AE related to the IC or SK procedure.
- Participants with at least one SAE related to the study participation or to the IC or SK procedure.
- Participants with at least one SAE leading to study discontinuation
- Participants with AE leading to death.

AEs and SAEs will be presented in tables by PT and sorted by decreasing frequencies on total, and broken down by maximum grade. AEs will be graded according to the NCI Common Terminology Criteria of Adverse Events (NCI CTCAE) Version 5.0.

Participants will be counted only once for each PT even if they have multiple records of the same PT. If a participant reports an AE more than once within that PT, the AE with the worst-case grade will be used in the corresponding grade summaries.

Document: \\ieedc-vnasc01\Biosdata\GSKGSK2857916\UZA78766\Biostatistics\Documentation\SAP\UZA78766_214098_SAP_v2.0_12OCT2022.docx

Author: PPD Version Number: 2.0
Version Date: 12OCT2022

Template No.: CS_TP_BS016 Revision 6

Reference: CS_WI_BS005

Effective Date: 02Dec2019

AEs leading to Death are those events which are recorded on the Adverse Events page of the parent study eCRF as at least one of the following criteria:

- AE Term: "Death"
- Outcome: "Death related to adverse event"
- Seriousness: Results in death
- Toxicity grade (CTCAE): Grade 5

[figure not shown]
AEs leading to death will be presented in a by-participant listing on the all-treated population.

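### SAP 17.2.1 puts procedure-related and participation-related SAEs in one by-method row, so no planned summary row gives procedure-related SAEs

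*Protocol*

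**What the plan says.** The secondary safety endpoint in Protocol Section 3 is tied to the procedure: "AEs associated with the impression cytology or SK procedure".

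Protocol 8.1.3 describes two classes of SAE with different causes and windows:

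- Procedure-related: "All SAEs related to the IC or SK procedure only will be collected from the start of intervention until the last follow-up visit".
- Related to study participation (the examples are the study intervention itself, procedures required by the protocol, and invasive tests): these "will be recorded from the time a participant consents to participate in the study".

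SAP 17.2.1 repeats both. Its overall summary table is shown by method of tissue collection on the ICSK population, that is, participants from whom a sample was taken. Two of its four rows concern relatedness: "Participants with at least one AE related to the IC or SK procedure" and "Participants with at least one SAE related to the study participation or to the IC or SK procedure". The other two count SAEs leading to discontinuation and AEs leading to death. The AE and SAE tables by preferred term are broken down by maximum grade, and no split by relatedness is stated.

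On causality, Protocol 10.2.4 says "The investigator is obligated to assess the relationship between study intervention and each occurrence of each AE/SAE". Protocol 10.2.5 repeats this duty, and separately asks for eCRF evidence of "review and verification of the relationship of each SAE to study intervention/study participation (causality".

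**The concern.** The endpoint asks what the IC or SK procedure does to participants. For serious events, the only relatedness row in the summary table answers a wider question: how many participants had an SAE attributed to anything in the study. Because study participation, as exemplified in 8.1.3, already includes the study intervention, the row amounts to all participation-related SAEs. Yet it sits under IC and SK columns, directly below an AE row that is limited to the procedure.

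Two things follow. The procedure-related SAE count cannot be read from any planned summary row. And an SAE caused by another study activity appears under a method that did not cause it. In a descriptive study with small columns, one such event is visible as a percentage.

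**Working it through.** The documents give no figure on this point, so there is none to reproduce. The check compares the rules and then shows the scale.

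**1. Does any summary row isolate procedure-related SAEs?**

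| Row in SAP 17.2.1 | Cause counted | Serious events only? | Isolates procedure-related SAEs? |
|---|---|---|---|
| Related AE | IC or SK procedure | No | No |
| Related SAE | Participation or procedure | Yes | No |
| SAE leading to discontinuation | Not stated | Yes | No |
| AE leading to death | Not stated | Fatal only | No |

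**2. Can the first two rows be combined to recover it?** Take an SK column of 5, and assume that the AE row includes serious events.

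- Case A: one participant has a serious procedure-related event. AE row 1/5, SAE row 1/5, true procedure-related SAEs 1/5.
- Case B: one participant has a mild procedure-related event, and another has an SAE related only to other participation. AE row 1/5, SAE row 1/5, true procedure-related SAEs 0/5.
- Case C: one participant has an SAE related only to other participation, with no procedure-related event in the column. AE row 0/5, SAE row 1/5, true procedure-related SAEs 0/5.

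A and B look the same in the table. C shows that the SAE row is not a subset of the AE row and can exceed it. The two rows give only an upper limit, the smaller of the two.

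**3. Can such an SAE reach an IC or SK column?** Yes. The Schedule of Activities (Protocol 1.3) places blood collection on the procedure day, and Protocol 6.8 places the sBCMA sample before the procedure. If that draw caused an SAE and the participant was then sampled, the participant is in the ICSK population and the event falls in that method's column. An SAE in someone never sampled does not enter the table.

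**4. Do the listings separate the two classes?** Partly. SAP 6.1 sets Day 1 as the day of procedure and computes study day from dates. Onset one day earlier gives study day -1, which is clear. A blood-draw SAE and a procedure SAE that both start on the procedure day have study day (0) + 1 = 1, so study day alone cannot tell them apart. A relatedness variable is needed.

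**5. Scale.** Assume a risk p of 0.1% to 1% per participant for an SAE related only to other participation. The documents give no rate. The chance of at least one among n is 1 - (1 - p)^n.

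- n = 5 (assumed SK column): 1 - 0.999^5 = 0.5%; 1 - 0.99^5 = 4.9%. One event moves the row from 0/5 = 0% (exact 95% CI 0% to 52.2%) to 1/5 = 20% (0.5% to 71.6%).
- n = 25 (enrollment cap, both methods together): 1 - 0.999^25 = 2.5%; 1 - 0.99^25 = 22.2%. One event moves the row from 0/25 = 0% (0% to 13.7%) to 1/25 = 4% (0.1% to 20.4%).

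Probability and column must use the same n: the 22.2% belongs with the 4% shift, not with the 20% shift. The SK column may exceed 5, since 5 is the target for evaluable samples.

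**The case against.** The strongest reply is that little is hidden. The row's label states its scope. All secondary safety data are listed by participant, at most 25 participants complete the procedure, and no test is planned, so a reader of the listings would find a single odd SAE. Table structure and footnotes are in output templates that were not supplied, and a split might be there. This stands as a reason for low priority. It does not supply the missing count: the SAP text names no such row, and step 4 shows that study day alone does not settle procedure-day events.

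Two stronger readings are tempting, and the documents do not support them.

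- From the slash in Protocol 10.2.5, a reader might infer that causality is captured as one undivided item. That sentence concerns evidence of review, such as a ticked box or signature, within 72 hours of SAE entry. The assessment duty is stated against the intervention alone, in 10.2.4 and again in 10.2.5: "The investigator is obligated to assess the relationship between study intervention and each occurrence of each AE/SAE/device deficiency". The eCRF layout is not in the documents.
- A reader might infer that SAEs with onset before the procedure will certainly be counted against IC or SK. Protocol 8.1.3 records participation-related SAEs from consent, but another of its bullets says that occurrences starting between consent and intervention are not collected, and the Schedule of Activities marks AE/SAE collection only from the procedure day. Whether such SAEs reach the database is unresolved.

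**Conclusion.** The point holds for the SAP table. The single SAE relatedness row mixes two classes that 8.1.3 keeps apart, no planned summary row gives the number of participants with a procedure-related SAE, and an SAE from another study activity in a sampled participant would appear under IC or SK. It does not establish a fault in how causality is recorded, nor that pre-procedure SAEs will be counted.

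The expected effect is small. On the assumed risk and an assumed SK column of 5, the chance that the SK row is affected at all is about 0.5% to 4.9%, though one event would then show as 20%. This is a low-priority correction that brings the table into line with the endpoint.

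**What to change.** In SAP 17.2.1, replace the combined row with two:

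1. participants with at least one SAE related to the IC or SK procedure, by method;
2. participants with at least one SAE related to other study participation only, in a total column.

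Flag the relatedness class in the by-method SAE table by preferred term.

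In Protocol 8.1.3, reconcile the bullet that records participation-related SAEs from consent with the bullet that excludes occurrences between consent and intervention, and bring the Schedule of Activities into line with the result.

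Confirm that the eCRF holds the two relationships separately. If it does, nothing changes there; if not, one further yes/no item is needed.

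The cost is one more table row and a sentence or two of text.

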10.3. Appendix 3: History of protocol changes

The Protocol Amendment Summary of Changes Table for the current amendment is located directly before the Table of Contents (TOC).

Amendment 1: 28-JUL-2020

Overall Rationale for the Amendment:

The protocol has been amended to update tear fluid specimen collection process and add a blood sample assessment at baseline.

Section # and Name	Description of Change	Brief Rationale
Objectives and Endpoints, Synopsis	Added Blood Sample Analysis	Add Analysis of blood BCMA levels
Multiple sections	Updated to include blood sample collection	Add Analysis of blood BCMA levels
1.3 Schedule of Assessments	Added Blood Sample Collection	Add Analysis of blood BCMA levels
3.0 Objectives and Endpoints	Added Blood Sample Analysis	Add Analysis of blood BCMA levels
4.2 Study Procedures	Added Tear Fluid & Blood Sample Analysis	Clarification
CCI		
6.6 Belantamab Mafodotin PK Sample Analysis	Added Section	Clarification
6.7 sBCMA Sample Collection and Analysis	Added Section	Clarification of specific lab testing

10.4. Appendix 4: Abbreviations and Trademarks

ADC	Antibody-drug conjugate
AE	Adverse event
ALT	Alanine aminotransferase
APRIL	A proliferation-inducing ligand
BAFF	B-cell activating factor family
BCMA	B-cell maturation antigen
BIB	Bioanalysis Immunogenicity and Biomarkers
BLys	B lymphocyte stimulator
CD38	Cluster of differentiation 38
CFR	Code of Federal Register
CI	Confidence interval
CIOMS	Council for International Organizations of Medical Sciences
CLW	Central Laboratory Worksheet
CMG	Case Management Group
CRF	Case Report Form
CSR	Clinical study report
CCI	
CV	Cardiovascular
DOE	Duration of Response
DREAMM	Driving Excellence in Approaches to Multiple Myeloma
eCRF	Electronic Case Report Form
GCP	Good Clinical Practice
GSK	GlaxoSmithKline
H&E	Hematoxylin-eosin
HIPAA	Health Insurance Portability and Accountability Act
IB	Investigator's Brochure
IC	Impression Cytology
ICF	Informed Consent Form
ICH	International Council for Harmonization of Technical Requirements for Pharmaceuticals for Human Use
IEC	Independent Ethics Committee
IgG	Immunoglobulin G
IgG1	Immunoglobulin G1
IHC	Immunohistochemistry
IMiD	Immunomodulatory drugs
ISS	Investigator Sponsored Study
kg	kilogram
MECs	Microcyst-like epithelial changes
mg	milligram
MM	Multiple myeloma
MMAF	Monomethyl auristatin-F
NCI	National Cancer Institute
OEF	Ocular eye findings
ORR	Overall Response Rate

PAS	Periodic acid-Schiff
PFS	Progression-free Survival
PR	Partial Response
QTL	Quality Tolerance Limit
Q3W	Every three weeks
RRMM	Relapsed/Refractory multiple myeloma
SAE	Serious adverse event
sCR	Stringent Complete Response
cci	
SoA	Schedule of activities
SRM	Study Reference Manual
ULN	Upper limit of normal
VGPR	Very Good Partial Response

Trademark Information

Trademarks of the GlaxoSmithKline group of companies	Trademarks not owned by the GlaxoSmithKline group of companies
NONE	Cytarabine Polytrim

1.1	12AUG2021	PPD	Minor updates to Appendix 1 – ensured section refers to 'Prior/Concomitant Ocular Therapy/Medications' and that references are to end of study not end of treatment.
1.2	12APR2022	PPD	
Updated to account for interim analysis (if 5 SK patients are not achieved by the planned final analysis timeline).
 
Definition of all-treated, ICSK populations updated.
 
Ocular history and risk factors summaries removed.
 
Summary for multiple myeloma disease characteristics removed.
 
Summary for histologic characterization removed.
 
Summary for corneal imaging and sensation removed.
 
Summaries for ocular examination and follow-up removed.
 
AEs and SAEs summaries to be presented by All-Treated not ICSK population.
 
Tear fluid summary updated to present detected/not detected (not quantitative data).

1.3	04MAY2022	PPD	Changed populations for primary, safety and

Document: \\ieedc-vnasc01\Biosdata\GSK\GSK2857916\UZA78766\Biostatistics\Documentation\SAP\UZA78766_214098_SAP_v2.0_12OCT2022.docx

Author: PPD Version Number: 2.0

Version Date: 12OCT2022

Template No.: CS_TP_BS016 Revision 6

Reference: CS_WI_BS005

Effective Date: 02Dec2019

		PPD	pharmacokinetics analyses.
1.4	07JUN2022		Added in pharmacokinetics populations.
1.5	13JUN2022		Removed PKTEAR, PKPLAS and PDBIO from reasons for exclusion summary within disposition table. Grammar corrections.
1.6	15JUN2022		SAP version and date updated. Grammar corrections.
2.0	12OCT2022		Addition of summary statistics to be reported for mAb for plasma results

Document: \\ieedc-vnasc01\Biosdata\GSK\GSK2857916\UZA78766\Biostatistics\Documentation\SAP\UZA78766_214098_SAP_v2.0_12OCT2022.docx

Author: PPD

Version Number: 2.0

Version Date: 12OCT2022

Template No.: CS_TP_BS016 Revision 6

Reference: CS_WI_BS005

Effective Date: 02Dec2019

TABLE OF CONTENTS

1. INTRODUCTION	9
2. STUDY OBJECTIVES.....	9
2.1. Primary Objective.....	9
2.2. Secondary Objectives.....	9
CCI	
3. STUDY DESIGN	10
3.1. General Description	10
3.2. Schedule of Activities	12
3.3. Changes to Analysis from Protocol.....	14
4. PLANNED ANALYSES	14
4.1. Final Analysis.....	14
5. ANALYSIS POPULATIONS.....	15
5.1. All Participants Screened.....	15
5.2. All-Treated Population.....	15
5.3. Impression Cytology or Superficial Keratectomy Procedure Population	15
6. GENERAL AND STATISTICAL CONSIDERATIONS	16
6.1. Reference Start Date and Study Day	16
6.2. Baseline.....	17
6.3. Unscheduled visits	17

